7.2.3 Safety Follow-up Visit

Upon permanent discontinuation from the study treatment for any reason, the following procedures will be performed approximately 30 (+7) days after the last dose of talimogene laherparepvec or the last dose of pembrolizumab, whichever is later. If an end of treatment decision occurs > 30 (+7) days after the last treatment date, then the safety follow-up should be performed as soon as possible (eg, within a week of the end of treatment decision). Applicable safety follow-up procedures should occur even if the subject has initiated new anticancer therapy.

Phase 1b and 3:

- Vital signs (systolic/diastolic blood pressure, heart rate, respiration rate, temperature): Subject must be in a supine position in a rested and calm state for at least 5 minutes before blood pressure assessments are conducted. If the subject is unable to be in the supine position, the subject should be in most recumbent position possible. The position selected for a subject should be the same that is used throughout the study and be documented on the vital sign CRF.

- Physical examination including body weight as per standard of care
- ECOG performance status assessment
- A 12-lead ECG. The ECG must include the following measurements: heart rate, PR, QRS, QT and QTc intervals.
- Local laboratory Assessments: Tests can be performed within 3 days of the planned visit.
 - hematology panel: hemoglobin, hematocrit, WBC count with 5-part differential (3-part differential if 5-part unable to be performed), RBC count, platelets
 - chemistry panel: sodium, potassium, chloride, calcium, magnesium, phosphorus, uric acid, total protein, albumin, BUN (phase 1b only), BUN/urea (phase 3), creatinine, total bilirubin, alkaline phosphatase, AST, ALT, glucose
 - LDH test (phase 3 only)
 - thyroid function tests: T3 (or FT3 per local standard), FT4, TSH
 - serum or urine pregnancy test for female subjects of childbearing potential
 - urinalysis (blood, glucose, protein, specific gravity) and reflexive microscopic exam only for any abnormal urinalysis results
- Central laboratory assessments:
 - Swab of cold sore, vesicles and other lesions suspected to be herpetic in origin (if any) for qPCR testing of talimogene laherparepvec DNA:
 - Upon notification of a suspected herpetic lesion by the subject, the subject should return to the clinic within 3 days of the occurrence of a reportable lesion suspected to be herpetic in origin. The lesion should be evaluated by the investigator and swabbed if HSV infection is suspected. A qPCR analysis will be performed on the swab sample to evaluate whether the talimogene laherparepvec DNA is detectable in the sample.
 - Blood for anti-pembrolizumab antibody (immunogenicity). Anti-pembrolizumab antibody sample collection and analyses in phase 3 may be discontinued if ongoing antibody results from this study continue to be consistent with existing antibody data from other pembrolizumab melanoma clinical trials.
 - Blood for PK pembrolizumab: sample taken at the same time as blood sample for anti-pembrolizumab antibody. Pembrolizumab PK sample collection and analyses in phase 3 may be discontinued if ongoing PK results from this study continue to be consistent with existing PK data from other pembrolizumab melanoma clinical trials.
- Recording of adverse events
- Recording of serious adverse events: Serious adverse events that occur within 90 (+7) days after the cessation of all study treatment or 30 (+7) days following cessation of treatment if the subject initiates new anticancer therapy, whichever is earlier, will be reported within 24 hours following the investigator's knowledge of the event.

Approved

- For subjects treated with pembrolizumab: Selected non-serious and serious adverse events known as pembrolizumab Events of Clinical Interest (ECI) must be reported to Amgen within 24 hours of the investigator's knowledge of the event regardless of attribution to pembrolizumab (see [Section 9.5](#)).
- Documentation of concomitant medications
- Completion of PRO (EQ-5D-3L and QLQ-C30) questionnaires

Phase 1b:

- Radiographic tumor imaging, clinical tumor assessment, photographic assessment, and tumor response assessments are to be performed if the subject ended study treatment prior to confirmed PD per modified irRC ([Appendix D](#)) and has not had assessments performed within 4 weeks (+1 week) of the visit.
 - Radiographic tumor imaging assessments must include CT scan, PET/CT, or MRI of the abdomen, pelvis, and chest along with all other sites of disease. In addition, CT scan or MRI of the brain will only be performed if signs or symptoms suggestive of CNS metastasis are present.
 - Photographic imaging assessments of visible cutaneous and subcutaneous lesions:
 - Photographs of visible cutaneous and subcutaneous index tumor lesions and of new visible lesion cutaneous and subcutaneous, if present.
 - Note: When a tumor lesion can be accurately evaluated by both, radiographic imaging and photographs, radiographic imaging evaluations should be undertaken.
 - Clinical tumor assessments must include clinical measurement of cutaneous, subcutaneous, or palpable nodal tumor lesions by caliper. Note: When a tumor lesion can be accurately evaluated by both, radiographic imaging and clinical examination, radiographic imaging evaluations should be undertaken.
 - Tumor response will be assessed using the modified irRC. Response (CR or PR) or PD to be confirmed by second consecutive response assessment no less than 4 weeks from the date of the first documented response or PD.

Phase 3:

- Radiographic tumor imaging, clinical tumor assessment, photographic assessment, and tumor response assessments are to be performed if the subject ended study treatment prior to confirmed iPD per modified irRC-RECIST ([Appendix F](#)) and has not had assessments performed within 4 weeks (+1 week) of the visit.
 - Radiographic tumor imaging assessments must include CT scan, PET/CT, or MRI of the abdomen, pelvis, and chest along with all other sites of disease. In addition, CT scan or MRI of the brain will only be performed if signs or symptoms suggestive of CNS metastasis are present.
 - Photographic imaging assessments of visible cutaneous and subcutaneous lesions:
 - Photographs of all visible (ie, visible protrusion from skin surface) cutaneous and subcutaneous tumor lesions not detectable on radiographic imaging must be performed.

- Note: When a tumor lesion can be accurately evaluated by both, radiographic imaging and photographs, radiographic imaging evaluations must be undertaken. When a lesion/lesions can not be evaluated by radiographic imaging, but can be accurately evaluated by both clinical examination and photographs, photographs must be undertaken. Photographs must also be taken for previously visible cutaneous and subcutaneous tumor lesions that have resolved at subsequent tumor assessment visits.
- Tumor response will be assessed using modified irRC-RECIST ([Appendix F](#)). Response (CR or PR) or iPD to be confirmed by second consecutive response assessment no less than 4 weeks from the date of the first documented response or iPD.

The Safety Follow-up visit is not required for those subjects who are randomized, but do not receive any doses of investigational product.

7.2.4 Long-term Follow-up

All subjects who permanently discontinue study drug for any reason other than withdraw of full consent will be contacted by clinic visit or telephone to assess survival, initiation of additional melanoma therapy, and whether any injected investigational product-related adverse events has occurred.

Contact for all subjects will be attempted every 12 weeks (\pm 28 days) following the safety follow-up visit until death, subject withdraws full consent, or up to 60 months after the end of randomization of phase 3. The sponsor may request survival status to be assessed at additional time points during the course of the study.

For subjects discontinuing study treatment without a documented confirmed PD, clinical tumor assessment (phase 1b only), radiographic imaging, photographic imaging, and tumor response assessment as detailed in [Section 7.2.2](#) and PRO (EQ-5D-3L and QLQ-C30) questionnaires will be performed every 12 weeks (+1 week) or more frequently if clinically indicated until documented confirmed PD per modified irRC in phase 1b ([Appendix D](#)) or iPD per modified irRC-RECIST in phase 3 ([Appendix F](#)), start of new anticancer treatment, death, or end of study, whichever occurs first. For subjects with progressive disease, QLQ-C30 will no longer be collected, and EQ-5D-3L will be collected through the long-term follow-up. Subjects who have reached a confirmed CR may increase their interval of radiographic assessments up to 6 months after the first 2 years beyond confirmed CR and up to 12 months after the first 5 years beyond confirmed CR as long as CR is maintained.

[figure not shown]
Approved

Blood for anti-pembrolizumab antibody and blood for PK of pembrolizumab will be collected at 3 and 6 months after study discontinuation or up until the subject starts new anticancer therapy, whichever occurs first. Anti-pembrolizumab antibody and pembrolizumab PK sample collection and analyses in phase 3 may be discontinued if ongoing antibody and PK results from this study continue to be consistent with existing antibody and PK data from other pembrolizumab melanoma clinical trials.

All subjects treated with talimogene laherparepvec (all phase 1b subjects and those who received talimogene laherparepvec in phase 3) and who permanently discontinue study will be eligible to continue follow-up for survival under an ongoing separate registry protocol that is in place for the long-term follow-up of subjects treated with talimogene laherparepvec in clinical trials. The registry protocol, including for phase 1b subjects, will not apply until the end of the study or 5 years after the last subject is enrolled in phase 3, whichever comes first. The registry protocol will also monitor for late and long-term adverse events thought to be potentially related to talimogene laherparepvec.

7.2.5 Reporting Unintended Exposure to Talimogene Laherparepvec in Phase 1b and Phase 3

If a household member, caregiver, or healthcare provider who has had close contact with the subject is suspected to have been exposed to talimogene laherparepvec (eg, has or who has had signs or symptoms suspected to be herpetic in origin or accidentally exposed to talimogene laherparepvec), report the potential or known unintended exposure to talimogene laherparepvec, suspected related signs or symptoms, and detection of talimogene laherparepvec in a subject's household member, caregiver, or healthcare provider as specified [Section 9.4](#).

[figure not shown]
Approved

7.3.1 Blood Samples

Blood samples are to be collected for [REDACTED] development as described in [Sections 7.2.2](#) and [7.2.3](#).

7.3.2 Archived Tumor Tissue Sample

A block of formalin-fixed paraffin-embedded tumor tissue collected prior to the study is to be sent to the central laboratory along with the corresponding pathology report (if available) as described in [Section 7.2.1](#). The tumor block is to be carefully selected by a pathologist or a skilled experienced histology associate to include generous tumor tissue using the Pathology Report as a guide. In lieu of a block, approximately 20 unstained sections on charged slides from the same block can be submitted. When the samples of tumor tissues are available, analyses of tumor specific mutations or epigenetic changes may be performed (eg, somatic mutations).

7.4 Pharmacogenetic Studies

If the subject consents to the optional pharmacogenetic portion of this study, DNA analyses may be performed. These optional pharmacogenetic analyses focus on inherited genetic variations to evaluate their possible correlation to the disease and/or responsiveness to the therapies used in this study. The goals of the optional studies include the use of genetic markers to help in the investigation of cancer and/or to identify subjects who may have positive or negative responses to talimogene laherparepvec and/or pembrolizumab. No additional samples are collected for this part of the study. For subjects who consent to this/these analysis/analyses, DNA may be extracted.

7.5 Sample Storage and Destruction

Any blood, tumor, or swab samples collected according to the Schedule of Assessments ([Table 5](#) and [Table 6](#)) can be analyzed for any of the tests outlined in the protocol and for any tests necessary to minimize risks to study subjects. This includes testing to ensure analytical methods produce reliable and valid data throughout the course of the study. This can also include, but is not limited to, investigation of unexpected results, incurred sample reanalysis, and analyses for method transfer and comparability.

Approved

All samples and associated results will be coded prior to being shipped from the site for analysis or storage. Samples will be tracked using a unique identifier that is assigned to the samples for the study. Results are stored in a secure database to ensure confidentiality.

If informed consent is provided by the subject, Amgen can do additional testing on remaining samples (ie, residual and back-up) to investigate and better understand the cancer, the dose response and/or prediction of response to talimogene laherparepvec and/or pembrolizumab, characterize antibody response, and characterize aspects of the molecule (eg, mechanism of action/target, metabolites). Results from these analyses are to be documented and maintained, but are not necessarily reported as part of this study. Samples can be retained for up to 20 years.

Since the qPCR testing of talimogene laherparepvec DNA from swabs of cold sores, vesicles, and other lesions suspected to be herpetic in origin are not expected to be available in time to benefit the subject directly or to alter the treatment course, the results of qPCR testing will not be provided unless requested by the investigator or the subject. Results may not be available until the end of the study. The evaluations of pharmacogenetic, [REDACTED] or other exploratory studies are not expected to benefit the subject directly or to alter the treatment course. The results of pharmacogenetic, [REDACTED] or other exploratory studies are not placed in the subject's medical record and are not to be made available to the subject, members of the family, the personal physician, or other third parties, except as specified in the informed consent.

The subject retains the right to request that the sample material be destroyed by contacting the investigator. Following the request from the subject, the investigator is to provide the sponsor with the required study and subject number so that any remaining blood and tumor samples and any other components from the cells can be located and destroyed. Samples will be destroyed once all protocol-defined procedures are completed. However, information collected from samples prior to the request for destruction, will be retained by Amgen.

The sponsor is the exclusive owner of any data, discoveries, or derivative materials from the sample materials and is responsible for the destruction of the sample(s) at the request of the subject through the investigator, at the end of the storage period, or as appropriate (eg, the scientific rationale for experimentation with a certain sample type no longer justifies keeping the sample). If a commercial product is developed from this

research project, the sponsor owns the commercial product. The subject has no commercial rights to such product and has no commercial rights to the data, information, discoveries, or derivative materials gained or produced from the sample.

See [Section 11.3](#) for subject confidentiality.

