5.2 Site Personnel Access to Individual Treatment Assignments

Talimogene laherparepvec or placebo may be supplied as open label or blinded product. Where talimogene laherparepvec or placebo is supplied open label, the site pharmacist or designee will need to be unblinded to prepare blinded talimogene laherparepvec/placebo. However, all precaution and efforts, including independent monitoring and tracked records, will be taken to ensure the Sponsor and blinded site personal will remain blinded to the study treatment.

- For talimogene laherparepvec or placebo supplied as open-label investigational medicinal product IVRS will confirm to the unblinded site pharmacist or designee from which lot number(s) vials must be selected for a patient visit. In no circumstances should an unblinded pharmacist reveal the treatment assignment to other site staff.
- For talimogene laherparepvec or placebo supplied as blinded investigational medicinal product IVRS will confirm to the site pharmacist or designee from which box number(s) vials must be selected for a patient visit. All site personnel will be blinded to study treatment.

A subject's treatment assignment should only be unblinded when knowledge of the treatment is essential for the further management of the subject on this study and/or for determining eligible treatment options outside of the trial after the subject discontinues study treatment due to documented disease progression. In the event that a subject's treatment assignment must be unblinded by the investigator using the IVRS unblinding

module, the subject will require review by the medical monitor to determine if they will be allowed to receive any further investigational product. Unblinding at the study site for any other reason will be considered a protocol deviation.

The principal investigator is strongly encouraged to contact the sponsor before unblinding any subject's treatment assignment, but must do so within 1 working day after the event and must document the unblinding in the subject's electronic case report form.

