6.2 Investigational Products

6.2.1 Amgen Investigational Product: Talimogene Laherparepvec or Placebo

Talimogene laherparepvec and placebo will be manufactured and packaged by Amgen Inc. and distributed using Amgen clinical study drug distribution procedures. The supply for the 10^6 PFU/mL concentration will be packaged separately from the supply for the 10^8 PFU/mL concentration.

Placebo (talimogene laherparepvec formulation excipients as described in the [Talimogene Laherparepvec Investigator's Brochure](#)) will be supplied as sterile frozen liquid is the same presentation, packaging and with blinded labelling as for talimogene laherparepvec.

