^l Blood samples for thyroid function tests (T3 [or FT3 per local standard], FT4, and TSH) will be collected at screening. Samples will be collected prior to study treatment administration on day 1 (-3 days) every 6 weeks until end of study treatment. Blood sample will also be collected at the safety follow-up visit (-3 days). Thyroid function tests must be collected, but if there are no symptoms of hypothyroidism or hyperthyroidism, study treatment can be initiated prior to the reporting of the laboratory results.

^m Urine or serum pregnancy test to be performed on female of childbearing potential. A urine pregnancy test should be performed within 72 hours prior to enrollment and at the safety follow-up. If urine pregnancy test result is positive or cannot be confirmed as negative, a serum pregnancy test will be required. Note: Additional (eg, monthly) on-treatment pregnancy testing should be conducted as required per local laws and regulations, where applicable.

Approved

Approved

^s Swab of any lesion of herpetic origin for qPCR testing of talimogene laherparepvec DNA: Upon notification of a suspected herpetic lesion by the subject, the subject should be instructed to return to clinic within 3 days of the occurrence of reportable lesion suspected to be herpetic in origin such as cold sores or vesicles. The lesion should be evaluated by the investigator and swabbed if HSV infection is suspected. The sample will be collected, stored, and ultimately tested for the detection of talimogene laherparepvec DNA using qPCR.

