7.2.2 Treatment Period

Treatment begins when the first dose of protocol-required therapies is administered to a subject.

The following procedures will be completed during the treatment period at the times designated in the Schedule of Assessments (Table 5 and Table 6). Study treatment should begin as soon as possible after enrollment via IVRS but no later than 5 days after

enrollment/randomization. Study treatment is to be administered after all other procedures are completed, unless otherwise stated during each visit that it is required.

[figure not shown]
Phase 1b and 3:

- Local laboratory assessments: Screening laboratory values may be used for treatment initiation assessment if completed within 3 days of study treatment initiation. On treatment tests can be performed within 3 days of the planned visit. Results should be reviewed prior to the administration of study treatment.
 - Coagulation: PT or INR and PTT or aPTT – as clinically indicated
 - Serum or urine pregnancy test for female subjects of childbearing potential: Additional (eg, monthly) on-treatment pregnancy testing should be conducted as required per local laws and regulations, where applicable.
- Central laboratory assessments:
 - Swab of cold sore, vesicles and other lesions suspected to be herpetic in origin (if any) for qPCR testing of talimogene laherparepvec DNA:
 - Upon notification of a suspected herpetic lesion by the subject, the subject should return to the clinic within 3 days of the occurrence of a reportable lesion suspected to be herpetic in origin. The lesion should be evaluated by the investigator and swabbed if HSV infection is suspected. A qPCR analysis will be performed on the swab sample to evaluate whether the talimogene laherparepvec DNA is detectable in the sample.
- Recording of adverse events at each visit
- Recording of serious adverse events at each visit. Serious adverse events will be reported to Amgen within 24 hours following the investigator's knowledge of the event.
- For subject treated with pembrolizumab: Selected non-serious and serious adverse events known as pembrolizumab Events of Clinical Interest must be reported to Amgen within 24 hours of the investigator's knowledge of the event regardless of attribution to pembrolizumab (see [Section 9.5](#))
- Documentation of concomitant medications at each visit

Phase 1b:

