10.3 Access to Individual Subject Treatment Assignments by Amgen or Designees

To guard against actual or perceived bias due to subjective decisions made by Amgen or Designee in light of potentially unblinding data captured during phase 3 of the study, the study team will comply with Amgen standard operating procedures that govern restricted and potential unblinding data access. Subject-level unblinding data will be available to an external independent biostatistics group that supports the DMC safety and efficacy reviews. The external DMC will be the primary reviewer of the unblinding results for interim safety, efficacy, and futility analyses prior to the primary analysis of OS (see [Section 10.4.3](#)). If the DMC recommends to stop the study due to safety concerns

or declares that an efficacy or futility criterion has been met, then the sponsor may unblind a restricted study team as deemed necessary.

Unblinding and potentially unblinding information for subjects and investigators should not occur prior to the study being unblinded for the primary analysis of OS except as specified (eg, [Section 5.2](#), [Section 9.2.1.2](#), and [Section 10.4.3](#)).

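### Section 7.5 gives out talimogene laherparepvec DNA results on request with no exception for the double-blind phase 3, in conflict with Sections 5.2 and 10.3

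*Protocol*

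**What the plan says.** Protocol Section 7.5 opens with "Any blood, tumor, or swab samples collected according to the Schedule of Assessments" and cites Tables 5 and 6, so it covers phase 3 swabs as well as phase 1b swabs. For suspected herpetic lesions it states that "the results of qPCR testing will not be provided unless requested by the investigator or the subject". The reason given is that results are unlikely to arrive soon enough to help the subject or change treatment. The next sentence adds: "Results may not be available until the end of the study". The section does not mention the phase 3 blind and does not refer to Section 5.2 or 10.3.

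The phase 3 schedule includes the swab. Table 6 footnote s in Section 7.1 says: "The sample will be collected, stored, and ultimately tested for the detection of talimogene laherparepvec DNA using qPCR". Section 7.2.2 repeats this for both phases: "A qPCR analysis will be performed on the swab sample to evaluate whether the talimogene laherparepvec DNA is detectable in the sample". Section 6.2.1 describes the placebo as the formulation excipients.

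The blinding rules are elsewhere. Section 5.1 blinds subjects, site staff and sponsor study staff, except where the protocol specifies otherwise. Section 5.2 allows site unblinding for two purposes: when it is essential for managing the subject, and to settle treatment options after documented progression. It then says: "Unblinding at the study site for any other reason will be considered a protocol deviation". Section 10.3 says: "Unblinding and potentially unblinding information for subjects and investigators should not occur prior to the study being unblinded for the primary analysis of OS". It allows for exceptions and names Sections 5.2, 9.2.1.2 and 10.4.3 as examples.

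**The concern.** A site that follows Section 7.5 as written may ask for the result of a cold-sore swab and receive one that indicates the subject's arm. Sections 5.2 and 10.3 say that this should not happen. Because Section 5.1 allows exceptions specified in the protocol, a site could reasonably take Section 7.5 to be one.

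Amendment 2 introduced the blind so that intralesional injections in only one arm would not bias the comparison. Outcomes that depend on the investigator are the most exposed if assignment becomes known:

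- clinical-instability calls, which remove the need to confirm iPD under modified irRC-RECIST
- continuation of treatment after first iPD
- attribution of adverse events to the injected product
- patient-reported outcomes
- choice of subsequent therapy

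The unblinding sensitivity analyses in SAP Sections 10.5.4.1 and 10.5.4.2 are triggered only by inadvertent SUSAR unblinding, so a subject unblinded through a swab result would fall outside them.

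**Working it through.** The plan gives no figure on this point, so the check sets the passages side by side.

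1. **Does the release rule reach phase 3?** Yes. Section 7.5 cites Table 6, and Table 6 footnote s places the swab in the phase 3 schedule for both arms. Nothing in Section 7.5 limits the rule to phase 1b.

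2. **What does a result reveal?** The assay targets talimogene laherparepvec DNA, and the placebo is excipients. Let p1 and p0 be the probabilities that a swab is positive in the active and placebo arms. Assume 1:1 randomization and equal chances of being swabbed.
   - After a positive result, the probability of active assignment is p1 / (p1 + p0). It starts at 1/2 and equals 1 only if p0 = 0. False positives, contamination or misallocated product make p0 greater than 0.
   - After a negative result with p0 = 0, the probability of active assignment is (1 − p1) / (2 − p1). This is below 1/2, but above 0 unless every active-arm swab is positive. A negative therefore shifts belief towards placebo without establishing it.

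   The documents give neither p1 nor p0, so these expressions cannot be evaluated further.

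3. **Do the blinding rules accommodate the release?** No. Curiosity about a swab result is not one of the two purposes in Section 5.2, and Section 7.5 is not among the examples in Section 10.3.

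4. **Do they clearly override it?** No. The exceptions in Section 10.3 are introduced as examples, Section 5.1 leaves room for other specified exceptions, and Section 7.5 cross-refers to neither section.

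5. **Do other passages close the gap?** Only in part.
   - Section 7.2 sends the assay to a central laboratory and keeps results off the CRFs. That restricts data flow but does not prevent a reply to a site.
   - SAP Sections 7.6 and 10.9 define how swab results are summarized and add no access rule.
   - The same paragraph of Section 7.5 bars disclosure of pharmacogenetic and other exploratory results except as the consent form specifies. A firm restriction was therefore available and was not applied to the swab assay.

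6. **Which endpoints are exposed?** Primary PFS uses blinded central review under modified RECIST 1.1, and OS is death from any cause. Clinical instability belongs to modified irRC-RECIST (Protocol Section 3.1.3.2 and Appendix F; SAP Section 6, Table 2), so it does not enter the definition of a primary PFS event.

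**The case against.** The strongest reply is that Section 7.5 operates under Sections 5.2 and 10.3 and lacks only a cross-reference. Testing appears to be deferred, since the footnote has samples stored and eventually tested and Section 7.5 warns of results as late as study end. Section 10.3 binds the study team to operating procedures on potentially unblinding data, which are not in these documents. Side effects probably give more clues than rare swabs: chills were reported in 53% versus 3% when talimogene laherparepvec was added to ipilimumab (Section 2.2), and in 48% in phase 1b (Section 2.4). Section 5.2 already allows unblinding to choose treatment after progression, which weakens the route through subsequent therapy. Accrual also appears complete, since Table 9 uses the actual enrollment rate, so the remaining benefit of a change may be limited.

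Much of this stands, and it limits the size of the point. It does not remove the conflict. A warning about lateness is not a prohibition, and chills are suggestive where a product-specific positive is close to decisive.

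A reader might infer that Section 7.5 lets sites bypass the sponsor and the medical monitor and that such releases would go undetected. The documents do not support that. They do not say who answers a request or how it is screened. Section 5.2 requires sponsor contact within 1 working day and an eCRF record when an assignment is unblinded. SAP Section 9.4 provides for tracking of important protocol deviations.

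**Conclusion.** The conflict is real and is in current protocol text. Section 7.5 allows release on request of a result that, when positive, points to the active arm, while Sections 5.2 and 10.3 forbid the equivalent disclosure. This goes beyond missing detail, because following the stated rule could itself give out unblinding information.

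The size is modest. Only subjects with a suspected herpetic lesion are swabbed, the documents give no lesion or positivity rate, and the number affected is probably small. The conclusion assumes that the assay is specific to the product and that the placebo contains no virus. False positives, contamination and misallocation remain possible, so a positive is not absolute proof. It would also be wrong to say that placebo subjects reveal nothing, because a negative carries some information.

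A reader might further infer that the primary results are compromised. The documents do not support that: direct effects on centrally reviewed PFS and on OS should be small. The exposure is in the investigator-dependent outcomes.

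**What to change.** Amend Section 7.5 so that individual phase 3 qPCR results for talimogene laherparepvec DNA are withheld from subjects, sites and the blinded study team until study unblinding for the primary OS analysis. Any earlier request should be handled and documented only through the Section 5.2 unblinding process. Cross-refer Section 7.5 to Sections 5.2 and 10.3, instruct the central laboratory accordingly, and leave phase 1b unchanged.

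Optionally, extend the SUSAR-unblinding sensitivity analyses in SAP Sections 10.5.4.1 and 10.5.4.2 to any documented early release of a positive result. Because swab results are not on the CRFs, release dates would have to be recorded for this.

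The cost is a small protocol amendment and a laboratory instruction. Under Section 12.1 an amendment needs investigator agreement and ethics approval, and Section 3.2 plans about 175 sites, so it could be bundled with the next substantive change. Subjects and sites would wait for a result that Section 7.5 already does not expect in time to benefit the subject or alter treatment. The Section 5.2 route stays open where knowing the assignment is essential.
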